Studies have shown that ACZ administered as a single 1000 mg IV bolus transiently enhances cerebral perfusion in healthy subjects (Sullivan et al., 1987; Vagal et al., 2009). Subjects challenged with IV ACZ had between a 30% to 60% increase in cerebral blood flow, as measured by Xenon-enhanced computed tomography scan, within 15 minutes of IV bolus (Sullivan et al., 1987). Another study using ultrasonography demonstrated that enhanced perfusion was sustained for at least 30 minutes with return to baseline measures within one hour (Hartkamp et al., 2012). This same dose and route of administration will be used in subjects with MS to determine the transient change to cerebral perfusion as quantified using MRI metrics as described in section 2.2.

Though ACZ IV transiently enhances cerebral perfusion, longer-term changes would be required to potentially impact lesion evolution. Daily or divided-daily infusions necessitate chronic IV access, pose increased risk to the patient and are impractical. Oral ACZ has been shown to also increase cerebral perfusion in patients with other neurologic disorders ("Acetazolamide Tablets | Drug Summary | PDR.net," n.d.) and might prove a practical and effective alternate chronic therapy for patients with MS.

ACZ has been used in daily divided doses up to a maximum of 4000 mg per day to treat pseudotumor cerebri (NORDIC Idiopathic Intracranial Hypertension Study Group Writing Committee et al., 2014). Participants in Stage 1b of this study will be given escalating divided doses of oral ACZ up to 1500 mg per day to determine both the magnitude of change to cerebral perfusion with each dose and define the optimum dose(s) for additional studies. In the final stages of this study (stage 2a and 2b), subjects will be treated with ACZ, as determined in stage 1b, for six consecutive months to determine if long-term change to cerebral perfusion alters the evolution of MS plaques into persistent black holes.

Rationale for Study Population

Multiple sclerosis affects predominantly persons between 15 and 55 years of age with females being nearly four-times as likely to be diagnosed with disease as males (Koch-Henriksen and Sørensen, 2010; Orton et al., 2006; Reingold, 2002). MS in the paediatric population is now better recognized and has been shown to differ from that in the adults in both clinical and radiologic presentation and evolution (Ghassemi et al., 2014; Renoux et al., 2007).

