The primary endpoint of this study will be to determine if therapy with oral divided-dose ACZ administered each day for week-long period results in at least 15% increase in CBF. Studies have shown between 10% - 15% decrease in cerebral perfusion in patients with relapsing MS (Adhya et al., 2006). Therefore, increases in CBF of at least 15% might result in change to lesion evolution. Baseline CBF measures will be compared to measures obtained at each dose escalation step using paired *t* test and Mann-Whitney test.

Determine the effect of long-term oral ACZ on lesion evolution. The key secondary endpoint of this study is to determine if long-term use of oral daily divided-dose with ACZ improves tissue integrity in a proportion of MS lesions.

MRI scans will be segmented using into white and gray matter, T2 and T1 lesion components and contrast-enhancing lesion component. Expert raters (I.V., S.D., L.F.), who are blinded to treatment arm (see section 6.1) will perform quality control of the automated segmentation and obtain quantitative measures of cerebral perfusion. The number and volume of T2 hyperintense and T1 hypointense lesion will be determined using MRIAP. The ratio of T1 hypointense/T2 hyperintense lesion will be determined for baseline and each crossover period and correlated with CBF, CBV and MTT measures obtained at similar times using the Spearman rank correlation.

Diffusion tensor imaging (DTI) is a reliable, validated technique that quantitatively measures molecular diffusivity within tissue and provides information about its microstructural integrity. DTI will be used to monitor tissue integrity and correlate change with increases in CBF following ACZ.

Tertiary Objectives

Several studies have quantitated transverse and longitudinal relaxation times within lesions and normal-appearing white matter and gray matter. These studies have shown that changes in both transverse and longitudinal relaxation can precede lesion formation and possibly better evaluate lesion evolution as compared to black hole volumes (Papadopoulos et al., 2010; van Walderveen et al., 1999a; Walsh et al., 2014; Warntjes et al., 2013). We will manually delineate regions of interest within lesions to obtain T2 and T1 relaxometry metrics. Lesions within areas with greatest change in CBF will be compared with those with least change. We anticipate a correlation between relaxometry measures and areas with varying CBF.

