- 16. Positive pregnancy test or inability or unwillingness to use effective means of birth control. Effective birth control is defined as:
 - Refraining from all acts of vaginal intercourse (abstinence)
 - Consistent use of birth control pills
 - Tubal sterilization or male partner who has undergone vasectomy
 - Placement of an IUD (intrauterine device)
 - Use, with every act of intercourse, of a diaphragm with contraceptive jelly and/or condoms with contraceptive foam
- 17. Presence of metallic objects implanted in the body that would preclude the ability of the subject to safely have MRI exams.
- 18. Psychiatric illness, mental deficiency, or cognitive dysfunction making compliance with treatment or informed consent impossible.

Withdrawal Criteria

Patients can be withdrawn at any time if the investigator concludes that it would be in the patients' best interest for any reason. Patients may voluntarily withdraw from the study for any reason at any time. They may be considered withdrawn if they state an intention to withdraw, or fail to return for visits, or become lost to follow up for any other reason. Protocol violations should not lead to patient withdrawal unless they indicate a significant risk to the patient's safety. If premature patient withdrawal occurs for any reason, the principle investigator must determine the primary reason for a patient's premature withdrawal from the study and record this information on the Unanticipated Problems Tracking Log.

For patients who are lost to follow-up (i.e., those patients whose status is unclear because they fail to appear for study visits without stating an intention to withdrawal), the investigator will show "due diligence" by documenting in the source documents steps taken to contact the patient, e.g., dates of telephone calls, registered letters, etc. In the case of death, a patient will be considered withdrawn.

Subject Replacement

Patients who prematurely withdraw will not be replaced.

TRIAL SCHEDULE

Visit Schedule:

Stage 1a – IV ACZ in MS Subjects											
Total of 10 subjects (5 healthy and 5 MS patients)											
	Day -7	0 min	15 min	30 min	120 min	240 min					
	Screen										
Treatment		1 gm	1 gm IV bolus ACZ administered								
		immedia									
H&P	Х										
CBC, CMP	Х										
Urine pregnancy	Х										
pCASL MRI		Х	Х	Х	Х	Х					
DSC MRI						Х					

Stage 1b –Oral ACZ dose-escalation in MS Subjects											
Up to a Total of 10 subjects											

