Stage 1b - Participants in this stage of the study will be given escalating divided doses of oral ACZ up to 4000 mg per day to determine both the magnitude of change to cerebral perfusion with maintenance daily oral ACZ therapy and to define the optimum dose(s) for additional studies. Stage 1b and 2 of the study will utilize extended release oral ACZ, distributed by Hermann Research pharmacy and self-administered by the subject.

r	500mg BID	1000 mg BID	1500 mg BID	2000 mg BID	_	Legend + MPL pCASI
W -1	w o	W 2	W 4	W 6	W 8	+ MSFC + EDSS
Screening	+	÷	+	+	+	
	±	‡	+ *	+ +	+ *	

Treatment and data collection for stage 1b will take 2.5 months for each enrolled subject. As many as two subjects can be evaluated during the month and we would anticipate that this portion of the study can be completed within twelve months.

Image analysis will be performed once each subject completes treatment. Cerebral perfusion measures will be determined for each dose by the same unblinded analyst (S.D.).

Stage 2a - This stage will continue to gather information about whether daily oral ACZ is tolerated and the kinetics of the treatment effect. Patients continue on the same dose for 12 consecutive weeks and undergo repeat imaging at predetermined intervals. Sustained treatment over a short duration will allow us to rapidly determine whether sustained treatment with ACZ can alter cerebral blood flow and will provide a go/no-go for future studies using this drug/paradigm. Patients will obtain MRI scans and clinical evaluations every 6 weeks with contrast-based scans repeated at 12 weeks.

Stage 2b - This stage will determine long-term tolerability and if tachyphylaxis is present with oral ACZ. Patients will continue on the same dose for 24 consecutive weeks and undergo repeat imaging at predetermined intervals. MRI scans and clinical evaluations will be obtained every 6

weeks with contrast-based scans repeated every 12 weeks.

Stage 3 - This stage is a prospective delayed-start design to evaluate the potential for ACZ to persistently enhance cerebral perfusion and impact the evolution of MS lesions. This pilot study is anticipated to lead to a larger randomized phase 3 clinical trial.

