Subjects will receive 1 gram bolus of IV ACZ and a second scan using pCASL sequences will be obtained within 15 minutes of infusion. Subjects will remain in the MRI gantry and receive a third scan to determine CBF at 30 minutes from time of infusion. Subjects will then be removed from the MRI gantry and allowed a break.

Subjects will again be placed on the MRI gantry and scout, 3DT1 and pCASL sequences obtained within 120 minutes from time of ACZ infusion. Subjects will then be removed from the MRI gantry and allowed a break. A final scan will be performed using the same sequences within 240 minutes from time of ACZ infusion.

Stage 1b:

Screening Visit – Subjects will receive a complete medical and neurological examination. In addition, all subjects will obtain CBC, CMP and, if female, urine pregnancy test.

Visit 1 – Subjects will receive non-contrast MRI brain using sequences previously described to ensure proper orientation and registration (scout, 3DT1), sequences necessary for segmentation using MRIAP (2D dual echo, 2D fluid-attenuated inversion recovery [FLAIR]) and pCASL sequences to determine CBF at baseline. Subjects will begin taking 250 mg oral ACZ twice daily and continue for two weeks. Subjects will be encouraged to call the PI with any adverse events (see sections 2.4b and 7.1.2) while on study drug.

Visit 2 – Prior to dose-escalation, subjects will receive non-contrast MRI brain sequences as described above to measure effect of previous oral daily divided dose of ACZ on CBF. Upon completion of MRI, subjects will begin taking 500 mg oral ACZ twice daily and continue for two weeks. Subjects will be encouraged to call the PI with any adverse events (see sections 2.4b and 7.1.2) while on study drug.

Visit 3 – Prior to dose-escalation, subjects will receive non-contrast MRI brain sequences as described above to measure effect of previous oral daily divided dose of ACZ on CBF. Upon completion of MRI, subjects will begin taking 1000 mg oral ACZ twice daily and continue for two weeks. Subjects will be encouraged to call the PI with any adverse events (see sections 2.4b and 7.1.2) while on study drug.

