In those unusual instances where adequate control is not obtained by the twice-a-day administration of acetazolamide extended-release capsules, the desired control may be established by means of acetazolamide (tablets or parenteral). Use tablets or parenteral in accordance with the more frequent dosage schedules recommended for these dosage forms, such as 250 mg every four hours, or an initial dose of 500 mg followed by 250 mg or 125 mg every four hours, depending on the case in question.

Acute Mountain Sickness:

Dosage is 500 mg to 1000 mg daily, in divided doses using tablets or extended-release capsules as appropriate. In circumstances of rapid ascent, such as in rescue or military operations, the higher dose level of 1000 mg is recommended. It is preferable to initiate dosing 24 to 48 hours before ascent and to continue for 48 hours while at high altitude, or longer as necessary to control symptoms.

HOW SUPPLIED

Acetazolamide Extended-Release Capsules, 500 mg are white to off-white pellets filled in empty hard gelatin capsules with orange opaque cap imprinted with "EP" in black ink and white opaque body imprinted with "107" in black ink and are supplied as follows:

Unit dose packages of 30 (3x10) NDC 68084-401-21

Storage and Drug Accountability

Acetazolamide tablets will be stored at room temperature (between 68°F to 77°F) as suggested by the manufacturer. Intravenous formulation of ACZ will be stored as lyophilized powder at the temperature specified above in the Hermann Research pharmacy. Lyophilized powder will be reconstituted prior to infusion by the pharmacy. All study medication will be stored at the Hermann Research pharmacy and dispensed as needed during study.

TREATMENT

Rationale for Selection of Dose

The ACZ challenge test, using 1000 mg IV ACZ, is a commonly utilized clinical tool in evaluating patients with chronic intracerebral occlusive disease and is a reliable predictor of critically reduced cerebral perfusion (Vagal et al., 2009). Oral doses as high as 4000 mg daily have been previously used in the NORDIC clinical trial (NORDIC Idiopathic Intracranial Hypertension Study Group Writing Committee et al., 2014).

Participants in this study will be treated with the highest tolerated dose of oral ACZ extended release capsules shown to exert the greatest effect on cerebral perfusion. This dose will also be utilized for an anticipated subsequent large phase 3 trial to determine clinical efficacy.

Study Drug Formulations

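### Stage 1b is meant to identify the dose with the greatest effect on CBF, but no planned analysis compares doses, and choosing the largest observed mean would overstate that dose's effect

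*Combined protocol and SAP*

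**What the plan says.** Under Treatment, Rationale for Selection of Dose, participants are to receive the "highest tolerated dose of oral ACZ extended release capsules shown to exert the greatest effect on cerebral perfusion". The next sentence carries that dose forward: "This dose will also be utilized for an anticipated subsequent large phase 3 trial to determine clinical efficacy".

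The evidence is to come from Stage 1b. Its purpose under Study Design is to measure the CBF change at each dose and "to define the optimum dose(s) for additional studies". Rationale for Doses Selected also takes the later-stage dose from Stage 1b, and the Stage 2b schedule table leaves its dose to Stage 1b. The Stage 1b schedule gives the size as "Up to a Total of 10 subjects".

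The analysis stated for these steps is in Primary & Key Secondary Objective: "Baseline CBF measures will be compared to measures obtained at each dose escalation step using paired" t tests and the Mann-Whitney test. The same section sets a 15% rise in CBF as the mark of interest but does not link it to dose choice. Sample Size and Statistical Methods deals with the randomised comparison and has no Stage 1b analysis.

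The dose passages disagree:
- Study Design has "escalating divided doses of oral ACZ up to 4000 mg per day", while Rationale for Doses Selected has "escalating divided doses of oral ACZ up to 1500 mg per day".
- The schedule table and the design figure show four steps starting at 500 mg BID. The visit text has five: at Visit 1, "Subjects will begin taking 250 mg oral ACZ twice daily and continue for two weeks".
- The Stage 2a schedule and the Stage 2b text in Rationale for Study Design already name 1000 mg BID. The Stage 3 text in that section names 1000 mg for the delayed-start group, without a frequency.

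**The concern.** Greatest effect is a statement about doses relative to each other. A test of each step against baseline asks whether CBF changed on drug. Every step could differ from baseline with no evidence that any step differs from another. The plan has no between-dose contrast, no dose trend and no stated outcome for doses that are not separated.

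Two consequences follow. A dose could reach the later stages and a phase 3 trial described as shown to be best when nothing in the plan could show it. And if the choice is made on the observed means, the mean at the chosen step is too high on average, because it was picked for being high. Later work planned around that mean would expect too large a CBF gain.

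**Working it through.** The plan gives no power, precision or selection rule for Stage 1b, so there is no stated figure to reproduce. The question is how a choice by largest observed mean would behave.

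**Inputs**
- n = 10, the Stage 1b maximum, all assumed to complete.
- k = 4 steps (schedule table) or 5 (visit text).
- SD of CBF change 30% and within-subject correlation 0.5, borrowed from the Stage 3 sample-size text. The documents give neither for Stage 1b.
- SD 15% as a lower value. This is an assumption, not a document figure.

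With scan-level SD 30 and correlation 0.5, the SD of a change from baseline is 30 × √(2 × 0.5) = 30. Changes that share one baseline scan then correlate 0.5 with each other.

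**Bias when all steps have the same true effect (null or flat)**

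Bias = E[max of k standard normals] × SD × √((1 − 0.5)/n), with E[max] = 1.029 for k = 4 and 1.163 for k = 5, and √(0.5/10) = 0.2236.
- SD 30: 1.029 × 30 × 0.2236 = 6.9; 1.163 × 30 × 0.2236 = 7.8.
- SD 15: 1.029 × 15 × 0.2236 = 3.5; 1.163 × 15 × 0.2236 = 3.9.

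Simulation agrees, and each of four equal steps is picked about 25% of the time. With no effect at SD 30, the largest mean reaches the 15% mark in 16% (four steps) or 19% (five) of trials. For one prespecified step the figure is 5.7%: SE = 30/√10 = 9.49, and 15/9.49 = 1.58.

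**Bias with a true linear rise (3.75, 7.5, 11.25, 15% over four steps), by simulation**
- SD 30: bias about 5.4 points; best step picked in 55% of trials.
- SD 15: bias about 1.7 points; best step picked in 76% of trials.

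**Sensitivity**
- Null or flat response, n = 10: 1.5 points at SD 10, correlation 0.8 between the changes and four steps; 11.0 at SD 30, correlation 0 and five steps.
- Five completers, SD 30, correlation 0.5: 9.8 (four steps) to 11.0 (five).

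**How well 10 patients can separate doses**
- The SE of a within-patient difference between two steps is 9.49 (SD 30) or 4.74 (SD 15).
- Tukey-adjusted 95% half-width, four steps and 27 df (q = 3.87): 3.87 × √(450/10) = 26.0 points at SD 30, and 13.0 at SD 15. The true gap between adjacent steps in the linear case is 3.75.
- Trend over the four active steps (weights −3, −1, 1, 3): contrast = −11.25 − 7.5 + 11.25 + 45 = 37.5. At SD 30, SE = √(450 × 20/10) = 30, ratio 1.25, power about 22% to 24%. At SD 15, SE = 15, ratio 2.5, power about 67% to 71%.
- Trend that also includes baseline: SE = √(450 × 10/10) = 21.2 at SD 30 and power about 40%, against 29% for the paired t test at the top step. But with the same 15% effect at every dose, it declares a trend in 28% (SD 30) to 79% (SD 15) of trials. It mixes drug against no drug with dose against dose.

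**The case against.** A reader might infer that the rule names a winning dose every time, even when the drug does nothing. The documents do not support that. It holds only for a bare maximum with no threshold, and the sentence also requires the highest tolerated dose. If tolerability decides, nothing is maximised over CBF and the selection bias is zero.

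The word shown, the 15% mark and the baseline tests could also act as a gate, although the plan never connects them to dose choice. With no true effect and four or five steps, a gate would name a dose in:
- 8% to 10% of trials if some step must reach p < 0.05;
- 0.3% (SD 15) or 16% to 19% (SD 30) if the best mean must reach 15%;
- 0.3% (SD 15) or 7% to 8% (SD 30) if both are required.

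Stage 2a adds a go/no-go, without a criterion. And naming one of several equally effective doses is not a false claim of efficacy.

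All of this stands against the stronger reading. It does not supply the missing comparison, because a gate tests drug against baseline. With a flat 15% effect at all four steps, a gate requiring the winner to have p < 0.05 and a mean of at least 15% passes in 54% (SD 30) or 80% (SD 15) of trials. The top dose is still the pick only 25% of the time. Given a pass, the overstatement is 12.1 or 4.9 points.

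The passages naming 1000 mg raise a real doubt about whether the Treatment sentence governs the later stages at all. If the dose is already fixed, the selection bias may not arise, but the greatest-effect wording still has no analysis behind it.

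Finally, these are small pilot stages. That limits what can be expected of them, and it is also a reason not to state a between-dose conclusion that they cannot reach.

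**Conclusion.** The concern holds in a limited form. As written, the plan cannot support the statement that the dose carried forward was shown to have the greatest effect on CBF. That follows from the documents alone and needs no numerical assumption.

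The upward bias is conditional on choosing by largest observed mean. It is then about 3.5 to 7.8 points under a null or flat response, and about 1.7 to 5.4 under a linear rise to 15% over four steps. These ranges rest on 10 completers, a correlation of 0.5 and SDs of 15% (assumed) to 30% (borrowed from Stage 3). Fewer completers would widen them, and the protocol withdraws subjects who cannot tolerate the drug.

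A reader might also infer that Stage 3's result would be inflated. It would not: Stage 3 compares the drug with concurrent placebo in its own data. What is affected is the Stage 1b estimate and any planning built on it.

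**What to change.** - Analyse all Stage 1b CBF scans in one repeated-measures mixed model.
- Report every pairwise between-dose difference with a 95% CI adjusted for multiplicity.
- Prespecify a linear trend across the active dose steps only, without baseline. Label it dose-or-duration, because dose and time on drug rise together in this escalation.
- Say a dose was shown to have the greatest effect only if its adjusted CIs against every other dose exclude zero in its favour. Otherwise report that Stage 1b did not separate the doses on CBF. Comparing the winner only with the next lower step would not do: it is undefined when the lowest step wins and says nothing about the remaining doses.
- Do not plan from the selected dose's raw mean without stating that it is subject to selection bias. A mixed model with dose as a category does not remove that bias; with complete data it returns the same mean.
- The sponsor should reconcile the Treatment sentence and the Stage 2b schedule with the passages that already name a dose, and reconcile the differing Stage 1b steps and maxima. No dose or clinical rule is proposed here.

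The cost is wording and one model on scans already scheduled, with no added patients or visits. The downside is that Stage 1b will usually report doses not separated. In the linear case, the top step would need an observed lead over the next step of about 26 points (SD 30) or 13 (SD 15). Against a true lead of 3.75, (26.0 − 3.75)/9.49 = 2.3 and (13.0 − 3.75)/4.74 = 2.0, so that comparison alone would succeed in roughly 1% or 3% of trials.
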